
I.5 *Specify your research question(s), study aims or hypotheses (do not indicate "see protocol")*

The objective of this application is to investigate the short- and long-term effects of multiple sessions of 4 mA M1 tDCS on fatigue and brain activity in recovered COVID-19 patients using established measures of perception of fatigue, performance fatigability, and cerebral glucose uptake. Our central hypothesis is that tDCS will improve fatigue short- and long-term, and thus will improve quality of life (QOL) in recovered COVID-19 patients and that these changes will be associated with alterations in brain activity.

Aim 1: Determine the short-term effects of multiple sessions of M1 tDCS on fatigue, and the subsequent influence on QOL, in recovered COVID-19 patients.

Hypothesis 1: Fatigue and QOL will significantly improve immediately after five consecutive sessions of M1 tDCS.

Aim 2: Determine the long-term effects of multiple sessions of tDCS on fatigue and the subsequent influence on QOL, in recovered COVID-19 patients.

Hypothesis 2: The improvements in fatigue and QOL of recovered COVID-19 patients will be present at 3- and 6-week follow-ups.

Aim 3: Determine the association between cerebral glucose uptake and changes in fatigue/QOL measures in recovered COVID-19 patients.

Hypothesis 3: Changes in cerebral FDG uptake will be correlated with improved fatigue and quality of life.

Aim 4: Determine the effects of multiple sessions of tDCS on vascular function (arterial stiffness, endothelial function), baroreflex function, and cognitive function in recovered COVID-19 patients.

Hypothesis 4: Improvements in vascular function (arterial stiffness, endothelial function), baroreflex function, and cognitive function immediately after five consecutive sessions of M1 tDCS, and at 3 weeks and 6 weeks.

I.6 *Background and significance and/or Preliminary studies related to this project. (do not indicate "see protocol")*

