- Healthy enough to complete the protocol based, on information obtained from a clinical exam and past medical history, such as cardiovascular disease.
- Comprehension of the protocol, as indicated by an ability to respond to questions about the study after reading the consent form.
- Able to use and be contacted by telephone
- Able to speak, read, and understand English, and complete questionnaires in English

Exclusion criteria

- Medical diagnosis or condition that is considered to be an absolute or relative contraindication to participating in exercise training, such as major renal, pulmonary, hepatic, cardiac, gastrointestinal, HIV, cancer (other than treated basal cell cancer), or neurological disorders
- History/presence of secondary conditions such as seizure disorders (or on medications known to lower seizure threshold), hydrocephalus, diabetes mellitus, or claustrophobia
- Alcohol dependence or abuse (>2 drinks/day), or present history of drug abuse (last six months)
- History of significant traumatic brain injury or hydrocephalus
- Pregnancy

Inclusion criteria (COVID-19 non-fatigue subjects):

- 18–80 yrs.
- Previous positive COVID-19 test
- >30 days since positive COVID-19 diagnosis
- Meet CDC guidelines (<https://www.cdc.gov/coronavirus/2019-ncov/hcp/duration-isolation.html>) for discontinuation of home isolation
- Do not meet the criteria for fatigue, based on the Chalder Fatigue Scale CFQ-11 case definition of fatigue
- Healthy enough to complete the protocol based, on information obtained from a clinical exam and past medical history, such as cardiovascular disease.
- Comprehension of the protocol, as indicated by an ability to respond to questions about the study after reading the consent form.
- Able to use and be contacted by telephone
- Able to speak, read, and understand English, and complete questionnaires in English

Exclusion criteria

- Medical diagnosis or condition that is considered to be an absolute or relative contraindication to participating in exercise training, such as major renal, pulmonary, hepatic, cardiac, gastrointestinal, HIV, cancer (other than treated basal cell cancer), or neurological disorders
- History/presence of secondary conditions such as seizure disorders (or on medications known to lower seizure threshold), hydrocephalus, diabetes mellitus, or claustrophobia
- Alcohol dependence or abuse (>2 drinks/day), or present history of drug abuse (last six months)

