During the first visit, the PI or research staff will provide potential subjects with the consent summary and full consent document. Subjects will be allowed to review the documents at their leisure and research personnel will answer all questions asked by the potential subject. The potential subject will be informed of all potential risks before signing the consent document. Subjects will in no way be coerced to sign the consent form and will be informed that it is their choice whether to volunteer for this study. Even after subjects sign the consent, they are free to withdraw from the study at any time for any reason. Consent may also be obtained via Zoom meeting or phone call prior to the Visit 1. After participant has been deemed eligible to participate in the study, research staff will conduct a zoom or phone call to walk through the study design and consent, as well as answer any questions the participant may have. Participants will then schedule their first five visits. After participants confirm their visit dates/times, they will be sent a confirmation email with detailed information about their visits, as well as a link to the consent form. Participant may then sign the consent document at the end of the Zoom or phone call and either scan email a copy or bring the signed consent with them to Visit 1.

During all study visits, all recommended precautions for mitigating the spread of COVID-19 during in-person research visits (e.g., face masks, face shields, extra cleaning before and after study visits, increased handwashing/sanitizing) will be followed as approved by our Departmental Executive Officer (DEO).

Mass emails to the University of Iowa and UHIC communities will be used to recruit participants who had a positive COVID-19 test 3 months or longer ago and who are either still having symptoms of post-COVID fatigue or are asymptomatic.

VII.D.37

Does the study include any form of deception (e.g., providing participants with false information, misleading information, or withholding information about certain study procedures)?

Examples:

- *Procedure includes a cover story that provides a plausible but inaccurate account of the purposes of the research.*
- *Participants will be provided with false information regarding the particular behaviors of interest in the research.*
- *Procedures include a confederate pretending to be another participant in the study.*

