Describe study populations separately if they will be participating in different procedures - include CONTROL population if applicable.

DESCRIBE:

- **What subjects will be asked to do/what happens in the study (in sequential order)**
- **The time period over which procedures will occur**
- **The time commitment for the subject for individual visits/procedures**
- **Long-term followup and how it occurs**

Symptomatic subjects will be asked to complete 7 lab study sessions. The first lab session will take approximately 3.5 hours, the fifth lab session will take approximately 2 hours, and the tDCS sessions will take approximately 30 minutes. In all, full participation will take approximately seven weeks, with three week breaks between Lab Sessions 5, 6, and 7. Asymptomatic subjects will be asked to complete 1 lab study session, lasting approximately 2 hours.

Vascular study: In the initial session (Day 1) all subjects will 1) be consented, 2) undergo a blood draw to evaluate interleukin-6 values, lipids, glucose and c-reactive protein, complete 3) pulse wave velocity testing (arterial stiffness); 4) carotid compliance/stiffness with ultrasound 5) brachial artery flow-mediated dilation (vascular endothelial function) 6) the Fatigue Assessment Scale (FAS), 7) the Fatigue Severity Scale (FSS), 8) the visual analog scale (VAS) for pain, 9) cognitive testing 10) 1-100 symptom scale, 11) international physical activity questionnaire (IPAQ), 12) Pittsburgh sleep quality index (PSQI), and 13) the 6-minute walk test. For asymptomatic participants, this will mark the end of their study participation. For symptomatic participants, they will then have their first round of the intervention receiving either sham or tDCS.

The following four days will include receiving either 20 min of tDCS or sham treatment, depending on group randomization. Day 5 will include the same testing battery (blood draw, PET scan in 10 subjects from each group [i.e., those that got the pre scan], questionnaires, fatigue testing, walking test) as Day 1, except the subjects will not repeat the MRI scan, strength testing, or receive tDCS.

LONG-TERM EFFECTS OF tDCS: Three- and six-weeks following Day 5, participants will repeat the testing battery conducted on Days 1 and 5.

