MRI: MR imaging will be conducted on a GE 750W 3T scanner using a 32-channel head coil. Anatomical images will include volumetric sagittal T1 MPRAGE (TI=900ms, TE=3.2ms, TR=8.5ms, flip angle=8%;, FOV=256x256x192mm, matrix=256x256x192, bandwidth= 250Hz/pixel, acceleration=2) and sagittal T2 CUBE (TE= 60ms, TR= 2500ms, echo train length=140, FOV=256x256x192mm, matrix=256x256x192, bandwidth=500Hz/pixel, acceleration=2) scans acquired using prospective motion correction (PROMO) and a 1.0 mm isotropic spatial resolution.

Questionnaires and physical testing (e.g., strength/fatigue) will be performed in the INPL. PET scanning will either start in PET Imaging Center (height/weight measurements, glucose/pregnancy testing, IV insertion) and then walk/wheelchair the subjects to PBDB (FDG administration, uptake, and PET scanning), or be exclusively performed in PBDB (to accommodate any potential UIHC research

restrictions) at the discretion of PET Imaging staff. MRI scans always take place in the research dedicated 3T MRI scanner in PBDB.

VII.E.7

Will you attempt to recontact subjects who are lost to follow-up?

No - those lost to followup will not be recontacted

VII.E.9

Will subjects be provided any compensation for participating in this study?

Yes

VII.E.10

Cash

No

VII.E.11

Gift Card

No

VII.E.12

Check

Yes

VII.E.13

Who will be providing the research compensation check to the subject?

Accounting Services directly via the e-Voucher system

VII.E.16

Other

Yes

VII.E.17

Describe:

Participants will receive parking vouchers for UIHC parking ramps for the duration of their visits.

VII.E.18

If you plan to compensate subjects using cash, checks or cash equivalent does your unit have a Cash Handling Procedure in place that has been approved by Accounting Services?

Yes

VII.E.19

Describe the compensation plan including

- ***Compensation amount and type per visit***
- ***Total compensation***
- ***Pro-rating for early withdrawal from study***

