Subjects who are part of the symptomatic group will be compensated \$120 for their time and effort upon completion of the first five visits of the study. Two follow-up visits will be compensated at \$25 per visit, for a total of \$170 for completion of the entire study. If the subjects withdraw before completing the entire study, they will be paid for each session they completed, as follows: blood draw/vascular assessment, \$30 each visit (\$60 total for baseline and post-tDCS testing), tDCS/SHAM sessions: \$15 each visit (\$60 total).

Subjects who are part of the asymptomatic group will be compensated \$35 for their time and effort upon completion of visit one.

VIII. Risks

VIII.1

What are the risks to subjects including

- ***emotional or psychological***
- ***financial***
- ***legal or social***
- ***physical?***

tDCS safety (only applicable to symptomatic participants): tDCS is a non-invasive brain stimulation technique in which a very weak electrical current is applied to the scalp. tDCS has been conducted on humans and animals for many years and no evidence has emerged to suggest that it is harmful or has ever induced a serious side effect. However, the safety of tDCS is dependent on current strength, electrode size, and stimulation duration. Accordingly, these parameters have been investigated to establish safe and effective stimulation parameters for tDCS applications in research involving human subjects. The only side effects that have been reported when proper guidelines are followed are a temporary headache, skin redness under the electrodes, and/or tingling, itching, and burning sensations in some subjects. For example, a 2008 review of the approximately 100 human tDCS studies up until that time on healthy adults and patients found that 64 of these studies reported no side effects, 24 studies reported a temporary itching or tingling under the electrodes in some subjects, and one study reported skin redness. Furthermore, these slight side effects were of equal occurrence in subjects that received placebo stimulation in 7 studies. In addition, only two subjects in these 100 studies reported a mild headache. Similar findings have recently

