The data that will be shared with the Medical University of South Carolina (MUSC) will be de-identified, age, race and ethnicity will be reported as required by NIH (see attached template that will be requested for reporting purposes) as part of a final report to MUSC.

X.7

Does your study meet the NIH criteria for a Certificate of Confidentiality or will you be applying for Certificate of Confidentiality?

No

XI. Data Analysis

XI.1

Describe the analysis methods you will use, including, if applicable, the variables you will analyze

The generalized estimating equation (GEE) framework will be utilized to assess changes over time in fatigue and quality of life measures. An interaction term between time and treatment will allow us to test the within- and between-treatment differences over all time points. Using histograms, variable distributions will be assessed to decide which link function to specify when modeling each outcome. To account for the inherent correlation that occurs in repeated measures data, we will cluster on subject ID. In addition to

examining the unadjusted relationship between the time-treatment interaction and each outcome, we will consider the addition of control variables, which will reduce the likelihood of unaccounted confounders. The control variables being considered for inclusion in the adjusted models are age, sex, and disease duration. For each outcome, models will be fit for all possible combinations of control variables. The predictor set that yields the smallest Akaike information criterion (AIC) will be considered the optimal control variable set to adjust associations between the main predictor and the outcomes. Statistical significance will be assessed at the $\alpha = 0.05$ level.

XI.2

Provide the rationale or power analysis to support the number of subjects proposed to complete this study.

The sample size calculation was based on the Fatigue Severity Scale data from our own preliminary data that assessed the effects of multiple sessions of 4 mA tDCS on fatigue in people with multiple sclerosis. The effect size of this difference = 0.91 (Cohen's d). With alpha fixed at 0.05, we would need 20 total subjects in each group (tDCS and SHAM; details below) to achieve 80% power in a two-tailed independent samples test. Therefore, to account for 20% data and subject attrition, we will recruit 25 subjects per group (150 total).

XII. Future Research

XII.1

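### VII.E.7 rules out recontact without defining 'lost', so retrievable week-3 and week-6 questionnaire scores and the reasons for loss may be given up; the likely effect is small and the remedy cheap

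*Combined protocol and SAP*

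**What the plan says.** VII.E.7 asks whether subjects lost to follow-up will be recontacted. The answer is "No - those lost to followup will not be recontacted". The available text gives no number of missed visits, no number of contact attempts and no visit window that would make someone lost.

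The visits most exposed are described in VII.E.6: "Three- and six-weeks following Day 5, participants will repeat the testing battery conducted on Days 1 and 5". Hypothesis 2 in I.5 depends on them: "The improvements in fatigue and QOL of recovered COVID-19 patients will be present at 3- and 6-week follow-ups".

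In VII.E.6 only symptomatic subjects have these visits. Of asymptomatic subjects it says: "For asymptomatic participants, this will mark the end of their study participation". The payment plan in VII.E.19 follows the same split. VI.13 and VII.E.2, however, describe randomising all three populations (fatigued, non-fatigued and never-infected) to tDCS or sham, 25 per arm in each, and VII.E.2 mentions nine sessions where VII.E.6 has seven.

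On contact, VI.13 requires every subject to be "Able to use and be contacted by telephone", and VII.D.9 and VII.D.29 allow consent by phone.

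On analysis, XI.1 specifies GEE clustered on subject: "An interaction term between time and treatment will allow us to test the within- and between-treatment differences over all time points". It names no working correlation, weighting or missing-data method. XI.2 derives 20 per group and recruits 25 to allow for 20% data and subject attrition.

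**The concern.** An explicit refusal to recontact is a choice, not an omitted detail. It has two costs. First, fatigue scores at weeks 3 and 6 are lost although a questionnaire could be completed by telephone with people selected for being reachable that way. Second, nobody learns why they left.

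The second cost matters for interpretation. Recruiting 25 to retain 20 restores precision but does nothing about who is missing. Unweighted GEE uses every observed visit, yet in general needs missed visits to be unrelated to the scores that would have been recorded. If more fatigued people leave one arm more readily than the other, the week-6 contrast moves. Without recorded reasons, a reader cannot judge whether that happened.

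**Working it through.** **1. The plan's own figure.** Inputs from XI.2: d = 0.91, two-sided alpha 0.05, 80% power, 20% attrition. The two-sample t-test solution is 19.96, so 20 per group; 20/(1 − 0.20) = 25. Both figures reproduce. Power is 88.3% with 25 evaluable per arm and 80.1% with 20. Loss within the allowance therefore leaves power at the planned level, and what remains is possible bias.

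**2. Who is affected.** Under VII.E.6 and VII.E.19, symptomatic subjects: 50 of 150 if that means the fatigue group (25 + 25). Under VI.13 and VII.E.2 the affected group could be larger.

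**3. Size of a bias, by formula.** The documents give no loss rate by visit and no relation between loss and fatigue, so these inputs are assumptions:
- 5 of 25 lost per arm, i.e. the whole 20% allowance taken as lost people
- correlation 0.5 between any two visits
- exchangeable working correlation
- 'link' = correlation between the tendency to be lost and fatigue; in this formula, the week-6 value

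Take a link of 0.5 in the tDCS arm only, with the more fatigued tending to leave. If the upper 20% of a standard normal tendency is removed, the cut is 0.842, the density there is 0.280, and the retained mean is −0.280/0.80 = −0.35.
- Retained week-6 mean: 0.5 × −0.35 = −0.175 SD.
- Retained mean at each earlier visit: 0.5 × 0.5 × −0.35 = −0.0875 SD.
- Lost after Day 5 (Days 1 and 5 observed): the model borrows 0.5/(1 + 0.5) = 1/3 from each, so the shift is 0.175 − (1/3)(0.0875 + 0.0875) = 0.117 SD.
- Lost after Day 1: 0.175 − 0.5 × 0.0875 = 0.131 SD.

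An independence working correlation would not borrow from earlier visits and would leave the full 0.175 SD.

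**4. Size by simulation of the GEE** (exchangeable, sandwich standard errors, four visits, 25 per arm, 20,000 runs per setting). False positives are upper-tail, favouring tDCS: nominal 2.5%, and 3.0% to 3.3% here with no link.

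| Lost per arm | Link (tDCS/sham) | Shift, SD | False positives |
|---|---|---|---|
| 5 | equal (0.5/0.5) | 0.00 | – |
| 5 | 0.3/0.2 | 0.01–0.03 | 3.4–3.8% |
| 5 | 0.3/0 or 0.5/0, mean post-baseline level | 0.04–0.09 | 3.9–5.6% |
| 5 | 0.3/0 or 0.5/0, week-6 value | 0.07–0.13 | 5.1–7.1% |
| 2 | one arm only | 0.02–0.06 | 3.5–4.9% |

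The largest simulated shifts, 0.115 and 0.127, agree with the formula's 0.117 and 0.131. If the link is in the sham arm instead, the shift goes against tDCS: with 5 lost per arm, power at d = 0.91 is 74% to 82%, against 84% to 85% with no link.

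**5. In proportion.** With visit correlation 0.5, the change score has variance 2(1 − 0.5) = 1, so the standard error of the between-arm contrast is √(2/25) = 0.28 to √(2/20) = 0.32. A shift of 0.13 is under half of that.

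**6. What contact could recover.** If calls recovered 3 of the 5 per arm (assumed), the one-arm shift falls to 0.01–0.05 SD, and power under uninformative loss rises from about 85% to 88%.

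**The case against.** The strongest reply is that VII.E.7 concerns people who are already lost. It does not bar a call or a new appointment after one missed visit. A reader might infer that the plan forbids any such call; the text is silent on missed visits and does not support that. This part of the objection stands, and it is why the loss is conditional on how the rule is applied.

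A reader might also infer that the payment plan encourages people to stop after Day 5, since $120 of the $170 is paid "upon completion of the first five visits of the study". The amounts do not show it: $120/5 = $24 per early visit on average, against $25 for each follow-up visit. Likewise, "Participants will then schedule their first five visits" in VII.D.29 does not show that later visits go unscheduled.

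The numerical objection also largely stands. A material shift needs informative loss concentrated in one arm of a trial described as double-blind and sham-controlled. Blinding makes that less likely, though it does not exclude it. Treating all of the 20% as lost people is the unfavourable case, because the allowance also covers lost data.

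What survives is that a direct question was answered with an unqualified 'No', and nothing in the available text provides for retrieving a missed outcome or its reason.

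**Conclusion.** The point holds as a modest one. As written, VII.E.7 gives up obtainable week-3 and week-6 questionnaire outcomes, and the reasons for loss, for anyone classed as lost, and that class is undefined. The expected bias is about 0 SD if any link between loss and fatigue is equal across arms. It reaches about 0.13 SD only with an assumed one-arm correlation of 0.5, 5 of 25 lost per arm, visit correlation 0.5 and an exchangeable working correlation; upper-tail false positives are then about 7% against about 3%.

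A reader might conclude that the rule biases the trial towards tDCS. The documents do not support that: they give neither the existence nor the direction of a link, and a link in the sham arm would work against tDCS. Nor is power at issue, since loss up to 20% is already allowed for. The affected population is the symptomatic subjects under VII.E.6 and VII.E.19, subject to the conflict with VI.13 and VII.E.2. This is a low-cost improvement to consider.

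**What to change.** Replace the answer in VII.E.7 with wording such as:

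> Yes. After a missed visit, existing staff blinded to arm make up to two telephone or e-mail attempts, record the reason, and offer the remaining assessments, including to participants who stopped stimulation. If the participant cannot attend, FSS and FAS (and EQ-5D-5L if collected at Day 1) are taken by telephone within a stated window, for example 7 days either side of the due date, and flagged as telephone. A participant is lost only if both attempts fail. Contact stops if consent is withdrawn.

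The EQ-5D-5L condition is needed because VII.E.4 lists the instrument but the Day 1 battery in VII.E.6 does not. The window must be set, since the available text gives none.

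Costs and limits:
- An IRB wording change and about 16 attempts (2 lost per arm × 2 arms × 2 visits × 2 attempts) to 60 (5 × 2 × 3 × 2). Follow-up payments are already within the $170.
- Telephone scores may differ from paper scores, hence the flag.
- Isokinetic, walking, vascular and PET measures cannot be recovered by telephone.
- Participants who stopped stimulation early may dilute the effect. If 3 recovered tDCS participants among 23 analysed had gained nothing, the effect falls by 0.91 × 3/23 = 0.12, to 0.79, and GEE power is 77% against 85% with nobody recovered. This does not apply to people lost after Day 5, who had completed stimulation.

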tDCS TREATMENT PROTOCOL: A tDCS device (Soterix) will deliver a small direct current through two sponge surface electrodes (5 cm × 7 cm) soaked with ~15 mL of NaCl saline. The positive electrode (anode) will be placed over the M1 representation of the weaker leg (as determined by the strength test), and the return electrode (cathode) will be placed above the eyebrow on the opposite side of the head.

tDCS BLOCK: The participants will receive tDCS for 20 min while seated comfortably and quietly in a room. The intensity will start at 0 mA and will be incrementally increased to the target intensity of 4 mA over the initial 30 seconds. At the 20-minute time point, the current will be gradually reduced to 0 mA over 30 seconds.

SHAM BLOCK: During the sham block, stimulation will ramp up over 30 seconds, remain at the target intensity for 30 seconds, and then will ramp down over 30 seconds during the first and last 90 seconds of the 20 minute stimulation period. This sham protocol has previously been shown to improve subject blinding integrity.

Brain activity PET Imaging with [18F]Fluorodeoxyglucose (FDG): A subset of 10 subjects from each group will be asked to fast for a minimum of 6 hours prior to the FDG administration. The blood glucose level will be checked and must be less than or equal to 200 mg/dL in order to proceed with the imaging. FDG (5 mCi ± 10% IV) will be administered and tracer uptake will take place in a quiet, darkened room with eyes open and ears unplugged. Attenuation correction imaging (either AC-CT or transmission imaging) will be performed with emission imaging equivalent to that used in the ADNI-3 protocol.

FDG PET Image Processing: FDG images will be analyzed by volume-of-interest (VOI) based on the individual's structural MRI (maximum probability atlas of Neuro Tool of PMOD Biomedical Image Quantification, version 4.1, PMOD Technologies, Ltd., Zurich, Switzerland) as well as using currently-available software tools designed specifically for the analysis of FDG images (e.g., NeuroQ (Syntermed, Inc.), PALZ (PMOD Technologies, LTD), MIM6, Neuro tool (v.6.6, MIM Software, Inc.). Partial volume-corrected image data will also be analyzed. Global metabolism will be determined by calculating the volume-weighted average of the standardized uptake values (SUV) of the intracerebral pixels. Mean, median and partial volume-corrected mean SUVs will be determined for each tissue type (GM, WM), lobe, and region using the Neuro Tool (PMOD).

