been reported in research and review articles (Nitsche et al. 2008; Hummel et al. 2008). Physiological studies have also assessed the safety of tDCS when applied within the aforementioned stimulation guidelines. For example, there was no neuronal damage as measured by serum neuron-specific enolase (Stagg & Nitsche, 2011) or MRI measures of edema using contrast-enhanced and diffusion-weighted MRI measures following administration of tDCS (Nitsche et al. 2004). Furthermore, tDCS did not negatively alter measures of neuropsychological function and EEG activity (Iver et al. 2005). Accordingly, rat studies using tDCS models emulating tDCS applied to humans (Liebetanz et al. 2009) showed that the current density needed to induce tissue damage or lesions was about 1429 mA/cm^2 , whereas the current densities used in human studies are between 0.04 and 0.08 mA/cm^2 and in this proposal is 0.011 mA/cm^2 . In conclusion, the probability is very unlikely that harm may occur (see above). Based on the available literature a slight headache should be the worst possible negative effect and should be very rare. In this case, non-prescription medication should relieve the headache within 1-2 hours.

Risk of Blood Draw: Subjects may experience some discomfort/bleeding from the blood draws. Other risks include bruising and infection. To minimize these risks, all blood draws will be performed by certified personnel at the CRU in the University of Iowa Hospital.

Carotid-femoral pulse wave velocity (PWV) and flow-mediated dilation: There are no known or foreseeable risks associated with the use of carotid-femoral pulse wave velocity or flow-mediated dilation. ECG electrodes may cause minor irritation to the skin.

Risks of performing motor tasks: There is potential for injury (muscle strain) resulting from the strength, fatigue, and walking tests. There is a 0.01% chance of death (in people who have heart problems), a 0.02% risk of cardiac arrhythmias that would require the subjects to go to the hospital (in people with heart problems), and a risk of an increase or decrease in blood pressure. Following participation, subjects may experience some muscle soreness. Muscle soreness tends to be more common for individuals who have not exercised recently. Other risks may include feelings of anxiety and/or stress induced by the experiment, which can lead to an increase in heart rate and blood pressure.

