There are no known risks associated with limited exposure to magnetic fields. Magnets of this strength have been in use for medical imaging for over 15 years. However, we will keep a record of the length of time participants were in the magnet, as well as the amount of radio waves used during that time.

Risks of Pulse Wave Velocity

There are no known risks associated with the use of a non-invasive pulse transducer for pulse wave velocity. ECG electrodes may cause minor irritation to the skin.

Risks of Carotid Echocardiography

There are no known serious risks associated with the use of carotid echocardiography. ECG electrodes may cause minor irritation to the skin.

Risks of Brachial Artery FMD test

There is a risk of mild discomfort on the forearm when the blood pressure cuff is inflated and a mild temporary sensation of “pins and needles” in the forearm and hand. This feeling is completely reversed within several minutes after the cuff is released with no permanent discomfort.

Risk Cardiovagal Baroreflex Sensitivity test

There are no known risks associated with the use of this test.

Although the risk is minimal, there is a risk for breach of confidentiality.

VIII.2

What have you done to minimize the risks?

- ***If applicable to this study ALSO include:***
 - ***How you (members of your research team at Iowa) will monitor the safety of individual subjects.***
 - ***Include a description of the availability of medical or psychological resources that subjects might require as a consequence of participating in this research and how referral will occur if necessary (e.g. availability of emergency medical care, psychological counseling, etc.)***

All risks will be minimized by using safe, well-established procedures and strict monitoring of each experimental session. Study staff will be in close proximity to each subject to help prevent/minimize fall risk and muscle strain. Furthermore, risk will be minimized by using stimulation parameters that are well described, within international guidelines, and within the range of those used in hundreds, if not thousands, of studies (see above).

The venous catheter will be inserted by an individual from the PET Center that is qualified, trained, and experienced at inserting venous lines.

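### Section VIII.1 prints the trial's current density as 0.011 mA/cm²; the treatment parameters give 0.114 mA/cm², which is above, not below, the human range cited in the same sentence

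*Combined protocol and SAP*

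**What the plan says.** Section VII.E.6 of the combined protocol and SAP describes the stimulation. Current passes through "two sponge surface electrodes (5 cm × 7 cm"), one serving as anode and the other as return electrode, and in the active arm it is "incrementally increased to the target intensity of 4 mA". The objective in I.5 also names 4 mA. No other electrode size or lower active intensity appears anywhere in the document.

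Section VIII.1, under tDCS safety, gives a rat lesion level of 1429 mA/cm² (as printed) and sets human work and this trial against it: "whereas the current densities used in human studies are between 0.04 and 0.08 mA/cm^2 and in this proposal is 0.011 mA/cm^2". The next sentence concludes: "In conclusion, the probability is very unlikely that harm may occur (see above"). Section VIII.2 then describes the stimulation parameters as "within the range of those used in hundreds, if not thousands, of studies (see above").

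**The concern.** The density in VIII.1 should follow directly from the current and electrode size in VII.E.6, and it does not. VIII.1 itself says that "the safety of tDCS is dependent on current strength, electrode size, and stimulation duration"; the first two of these are the inputs to the density. The figure is also the form's only numerical placement of this trial's dose against human studies. A reader of VIII.1 alone would take the trial to be gentler than usual practice. If the true density is above the cited range, an ethics board is weighing risk on a comparison that runs the wrong way, and a safety conclusion that points back to the preceding text rests partly on it.

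**Working it through.** **Inputs**

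- Current: 4 mA (VII.E.6, tDCS block; also I.5).
- Electrode: 5 cm × 7 cm, so 35 cm² (VII.E.6, treatment protocol).
- Printed density for this trial: 0.011 mA/cm² (VIII.1).
- Cited human range: 0.04 to 0.08 mA/cm² (VIII.1).
- Rat lesion level as printed: 1429 mA/cm² (VIII.1).

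**Step 1: try to reproduce the printed figure.** Density = current / area.

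- 4 mA over one electrode: 4/35 = 0.114 mA/cm².
- 4 mA over both electrodes together: 4/70 = 0.057.
- 2 mA over one electrode: 2/35 = 0.057.
- 1 mA over one electrode: 1/35 = 0.029.
- Dimensions misread as inches (225.8 cm²): 4/225.8 = 0.018.
- 0.4 mA over one electrode: 0.4/35 = 0.0114.

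Only the last line gives 0.011, and it needs a tenth of the planned current. Put the other way round, 0.011 mA/cm² at 4 mA needs 4/0.011 = 364 cm² of electrode, and at 35 cm² it needs 0.011 × 35 = 0.385 mA. Neither is in the plan.

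**Step 2: size of the error.** 0.1143/0.011 = 10.4.

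**Step 3: position against the cited human range.**

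- As printed: 0.04/0.011 = 3.6 and 0.08/0.011 = 7.3, so the trial appears to lie 3.6 to 7.3 times below the range.
- As calculated: 0.1143/0.08 = 1.43 and 0.1143/0.04 = 2.86, so the trial is about 1.4 times the top and 2.9 times the bottom.
- In current terms, on 35 cm² the range corresponds to 0.04 × 35 = 1.4 mA up to 0.08 × 35 = 2.8 mA. The planned 4 mA is above both.

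**Step 4: position against the rat level as printed.** 1429/0.011 is about 130,000; 1429/0.1143 is about 12,500. The margin shrinks tenfold but keeps its direction.

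**The case against.** The strongest reply is that this is a decimal slip in a narrative, and that little depends on it. Much of that stands.

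- The dose is never hidden. The 4 mA intensity appears in the objective (I.5), the background (I.6), the treatment description (VII.E.6) and several study titles in VII.B.32, one of them on tolerability at 4 mA. I.6 also cites work supporting the safety of currents up to that level.
- The conclusion in VIII.1 does not rest on density alone. It follows a review of about 100 studies and evidence from a serum marker, MRI, neuropsychological testing and EEG.
- VIII.2 gives no density. It speaks of stimulation parameters generally and of international guidelines, so it does not restate the wrong figure.
- Using the combined area of both electrodes gives 0.057, inside the cited range. This is not the usual definition, because the full current passes through each electrode, and it does not give 0.011 either.

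Three stronger readings are tempting, and the document does not support them. First, a reader might infer that the reassurance about headache comes from the density comparison. The form gives another basis: "Based on the available literature a slight headache should be the worst possible negative effect and should be very rare". Second, a reader might infer that the non-significant-risk request falls. Its rationale in VII.B.31 is prior use of the device without serious side effects, with two attachments that are not available here; density plays no part. Third, a reader might infer that side effects would go unrecorded because VII.E.4 lists no tDCS side-effect form. That list covers instruments that obtain data directly from subjects, so staff records need not appear in it, and VIII.2 promises monitoring of every session. In any case that question is separate from the density error.

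None of this rescues 0.011 mA/cm² or the below-range comparison.

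**Conclusion.** The point holds as an error in the risk text. The density is 0.114 mA/cm², 10.4 times the printed value, and the comparison with human studies is reversed: the trial is about 43% over the top of the cited range, not below its bottom. The conclusion in VIII.1 loses one of its supports, and the within-range statement in VIII.2 does not fit the only numerical density range that VIII.1 gives.

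This assumes that density means the full current over one electrode, and that the cited human range was worked out in the same way; the document does not say how it was. The range and the rat level are taken as printed, since their sources cannot be checked here.

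A reader might go on to infer that 4 mA is unsafe. The document does not show that. Exceeding a cited range is not evidence of harm, the margin to the rat level as printed remains about 12,500-fold, and separate 4 mA work is cited. No dose, endpoint, analysis or sample size changes. The correction should still be made, because a stated safety comparison is wrong in direction and cheap to put right.

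**What to change.** 1. In VIII.1, replace the density clause for this trial with: *in this proposal is 0.114 mA/cm² (4 mA over 35 cm²), about 1.4 times the top of that range*.
2. Rest the conclusion in VIII.1 and the range statement in VIII.2 on the 4 mA safety and tolerability studies already cited in I.6 and VII.B.32, stating what those studies reported.
3. Check the consent text, which is not available here, for the same figure.

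The cost is a few sentence edits, a consent check and one IRB amendment. The downside is a less reassuring risk section and possible questions from the IRB. Trial conduct need not change.
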